
Sample Size
	
Registry
 
 
• Recruitment will continue until 1,500 participants meet the final Registry Cohort Criteria, unless the Executive Committee terminates recruitment due to feasibility.
 
• A maximum of 150 participants in Vision Cohort 3.
 
• A maximum of 100 participants where Inheritance Pattern is Recessive and phase is unknown.
 
• A maximum of 100 participants within gene.
 
 
The Executive Committee will monitor enrollment distributions across genes, inheritance patterns, vision cohorts, and age cohorts with the planned caps as noted. Enrollment in some genes, inheritance patterns, vision cohorts, or age cohorts may be encouraged to ensure appropriate representation, and some caps may be adjusted if needed.
 
Natural History Study
 
 
• The Natural History Study sample size for each gene will depend on the Registry enrollment; a maximum of 100 participants within gene.
 

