#### 638 **4.3.2 Vision Cohorts 1 & 2**

- 639 1. Medical updates to include:
  - 640 ♦ New or changed adverse events (AEs)
  - 641 ♦ New ocular procedures
  - 642 ♦ New or changed medications
- 643 2. Patient Reported Outcomes (PROs)
  - 644 ♦ **Adults (18+ years at Baseline):** PROMIS®-29, MRDQ, ViSIO-PRO
  - 645 ♦ **Adolescents (12-17 years at Baseline):** LVP-FVQ II, ViSIO-PRO
  - 646 ♦ **Children (8-11 years at Baseline):** LVP-FVQ II, ViSIO-ObsRO
  - 647 ♦ The PROs may be completed in person or remotely (phone or other remote  
 648 methods) any time within six (6) months of the Baseline Visit (not required to be  
 649 the same day as the rest of the Baseline Visit).
- 650 3. Complete ophthalmic examination to include:
  - 651 ♦ Slit lamp biomicroscopy
  - 652 ♦ Indirect ophthalmoscopy
  - 653 ♦ *If the Baseline Visit date is within 3 months of the Registry/Screening Visit*  
 654 *testing date and the ophthalmic examination was performed during the*  
 655 *Registry/Screening Visit (i.e., not historical) – the ophthalmic examination*  
 656 *testing procedure may be skipped.*
- 657 4. Visual Acuity (including refraction, ETDRS, BRVT if needed, LLVA if needed)
  - 658 ♦ The visual acuity (VA) letter score will determine whether LLVA or BRVT will  
 659 be performed. The criteria are defined in the **Uni-Rare Clinical Site Manual of**  
 660 **Procedures.**
  - 661 ♦ *If the Baseline Visit date is within 3 months of the Registry/Screening Visit*  
 662 *testing date – the VA testing procedure may be skipped.*
- 663 5. Intraocular Pressure (IOP)
  - 664 ♦ IOP measurements are to be taken prior to pupil dilation.

- 665           ♦ ***If the Baseline Visit date is within 3 months of the Registry/Screening Visit***  
666           ***testing date – the IOP testing procedure may be skipped.***
- 667       6. Color Vision
- 668           ♦ Desaturated (Lanthony D15)
- 669       7. Contrast Sensitivity
- 670       8. Spectral Domain Optical Coherence Tomography (SD-OCT)
- 671           ♦ Volume Scan
- 672           ♦ Vertical and Horizontal Scan
- 673           ♦ ***If the Baseline Visit date is within 3 months of the Registry/Screening Visit***  
674           ***testing date – the SD-OCT testing procedure may be skipped.***
- 675       9. Axial Length and Corneal Curvature Measurements
- 676       10. Optos Color Photos\*
- 677       11. Optos Fundus Autofluorescence (FAF)\*
- 678       12. Full-field Electroretinogram (ffERG)\*

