1215 ➤ **Figure 9-1** evaluates the **power to detect differences** in percent change from baseline to  
 1216 four (4) years among two (2) subgroups of equally distributed sizes, under various  
 1217 assumptions of true mean difference (x-axis) and standard deviation (SD) of the  
 1218 distribution of percent change. If subgroups are not equally sized, the smallest detectable  
 1219 difference (with the same power) will be larger. All calculations are based on a Type I ( $\alpha$ )  
 1220 error rate of 0.05.

1221 ○ For example, with a total sample size of twenty (20), assuming ten (10) in each of  
 1222 two (2) subgroups, to have power of 80% or more, the true difference needs to be  
 1223 approximately 1.25 SDs (a mean difference of 25% if the SD of the percent  
 1224 change over four (4) years 20%)

1225 ➤ **Also Note:** *Within-subgroup* point estimates and CIs will also be important. **Table 9-3**  
 1226 above can be applied to potential subgroup sample sizes as well to consider the precision  
 1227 that would be observed.

1228

1229

[figure not shown]
1230

1231

[figure not shown]
1232

1233 **Figure 9-1 Power to Detect Differences in Subgroups**

1234

1235

1236 **NHS Sample Size Example**

1237 The following is an example template of using the tables above and a set of assumptions for a  
 1238 given gene of interest to determine the impact on NHS Objectives.

Target Gene	MYO7A
Target Sample Size	50
Data to consider for assumptions	
Data
 
 
• RUSH2A Data – Mean (SD) percent change at 24M 
 
○ Visual Acuity: -2.3 (5.1)%
 
○ OCT EZ area: -2.2 (21.8)%
 
○ Static Perimetry HOV: -12.4 (28.2)%
 
 
 
 
Assume:
 
 
• Inter-eye correlation = 0.8
 
• SD for percent change at 4 years                     
 
○ Visual Acuity → 5%
 
○ OCT EZ area → 20%
 
○ Static Perimetry HOV → 30%
 
 
 

NHS Objective 1 (Natural History)	The half-width of a 95% CI around the point estimate for mean percent change at 4 years would be		
	Visual Acuity	OCT EZ area	Static Perimetry HOV
	1%	5%	8%
NHS Objective 2 (Structure-Function Relationship)	The 95% CI around correlation between any two outcome measures would be		

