1324 **NHS Objective 2 (Structure-Function Relationship)**

- 1325 ➤ **NHS Objective 2** is to explore whether structural outcome measures can be validated as  
 1326 surrogates for functional outcomes in individuals with disease-causing genetic variants,  
 1327 **within gene** (*where sample size 20 or more*).
- 1328 ○ **Analysis plan:** Scatterplots and Spearman correlation coefficients of changes in  
 1329 functional and structural outcome measures of progression from baseline to each  
 1330 visit will be evaluated.

1331 **NHS Objective 3 (Risk Factors for Progression)**

- 1332 ➤ **NHS Objective 3** is to explore possible risk factors (genotype, phenotype,  
 1333 environmental, and comorbidities) for progression of the outcome measures at 4 years in  
 1334 individuals with disease-causing genetic variants, **within-gene** (*where sample size 40 or*  
 1335 *more*).
- 1336 ○ **Analysis plan:** The distribution of each outcome in terms of both absolute  
 1337 change and percent change from baseline to 4 years will be summarized  
 1338 (including tabulating categorically, as well as means, standard deviations,

1339 medians, quartiles), stratified by categorical levels of each potential risk factor  
 1340 of interest (listed below). Potential risk factors to evaluate include:

- 1341 ○ Phenotypic:
  - 1342 ■ Clinical diagnosis (if applicable)
  - 1343 ■ Duration of disease
  - 1344 ■ Age of onset of initial vision symptoms
  - 1345 ■ Gender
  - 1346 ■ Race/ethnicity
  - 1347 ■ Visual Acuity
  - 1348 ■ Lens Status (phakic/pseudophakic/aphakic)
- 1349 ○ Genotypic:
  - 1350 ■ Characterizations of the variants
- 1351 ○ Environmental factors
  - 1352 ■ Smoking status at baseline
  - 1353 ■ Vitamin A use at baseline
  - 1354 ■ Docosahexaenoic acid (DHA) use at baseline
  - 1355 ■ Lutein use at baseline

1356 **Other Planned Analyses**

- 1357 ➤ Analysis plan for variability of repeat perimetry testing at baseline: Scatterplots and  
 1358 Spearman correlation coefficients for pairs (first versus second) of testing values for each  
 1359 repeated perimetry test. Bland-Altman plots of difference versus the mean value will be  
 1360 inspected. The intraclass correlation coefficient of the values and the within-eye variance will  
 1361 be estimated.
- 1362 ➤ Analysis plan for the symmetry of left eye versus right eye: At baseline and each subsequent  
 1363 testing time, the symmetry of the test result values from the left and right eyes will be  

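### NHS Objective 3 tabulates letter change in acuity by acuity level; if one Baseline reading serves both purposes, test noise alone makes better-acuity strata appear to lose more (about 0.1 to 1.0 letter)

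*Protocol*

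**What the plan says.** Protocol 9.2.2, NHS Objective 3, applies to genes "where sample size 40 or" more. The summary covers every outcome ("The distribution of each outcome in terms of both absolute" "change and percent change from baseline to 4 years will be summarized"), "medians, quartiles), stratified by categorical levels of each potential risk factor". The phenotypic factors include "Visual Acuity". The environmental factors are each dated to baseline; acuity is not.

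Acuity is also an Objective 3 outcome: the NHS Sample Size Example in 9.1.3 gives it a detectable subgroup difference of 4%.

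Three other provisions bear on the point:
- In 4.3.2 item 4, if Baseline falls within 3 months of the Registry/Screening test, "the VA testing procedure may be skipped", so the Registry reading can become the Baseline reading.
- Objective 1 averages tests performed more than once, but at Baseline only static perimetry and microperimetry are repeated, not acuity.
- The footnote to 2.4.2 exempts the Younger Age Cohort from Registry acuity testing.

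**The concern.** When one noisy reading both places an eye in a stratum and is subtracted to form its change, the two are negatively linked by construction. An eye that reads high by chance enters the better stratum and then seems to decline; an eye that reads low enters the worse stratum and seems to improve. This is regression to the mean in a change score. It does not arise when acuity is used as a factor for change in EZ area or the hill of vision, because those outcomes do not contain the acuity reading.

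Nothing in 9.2 removes it. Acuity is not excluded as a factor for its own change. The model adjusted for baseline differences is for patient-reported outcomes, and the ANCOVA in 9.2.1 is for cross-sectional Registry data. The protocol's précis names well-defined subpopulations for future trials as an expected product, so a false impression that better-seeing eyes lose acuity faster could feed into that choice.

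**Working it through.** **The plan's own figure.** The 9.1.3 example uses 25 per subgroup, inter-eye correlation 0.8, alpha 0.05 and 80% power. Effective n per group = 25 x 2/1.8 = 27.8. Detectable difference = SD x sqrt(2/27.8) x (1.960 + 0.842):
- SD 5%: 3.76%
- SD 20%: 15.03%
- SD 30%: 22.55%

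These round to the stated 4%, 15% and 23%.

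**Inputs**
- Baseline acuity mean 77.9, SD 11.7 letters (9.1.2 Registry example): variance 136.9.
- Assumed SD of 4-year change 5% (9.1.3): 0.05 x 77.9 = 3.9 letters.
- Mean 24-month change -2.3% (9.1.3, the entry beginning "Visual Acuity: -2.3 (5.1"): 0.023 x 77.9 = 1.8 letters lost.
- Within-gene N from 40, the Objective 3 threshold, to the cap ("A maximum of 100 participants within gene").
- Test-retest SD: not given. If all the change variance were noise, error variance per reading would be 3.9²/2 = 7.6 (SD 2.75). This is an upper bound. Half and a quarter of it are taken as further cases.

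**Formula.** With no true association, the slope of change on the shared reading is -(error variance)/(observed variance). The upper and lower halves of a normal variable differ by 2 x 0.798 x SD.

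Single eye, all noise: gap between halves 2 x 0.798 x 11.7 = 18.7 letters; artefact 18.7 x 7.6/136.9 = 1.04 letters.

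Mean of two eyes: observed variance 136.9 x (1 + 0.8)/2 = 123.2, SD 11.1, gap between halves 17.7 letters. Error variance of the mean is 7.6 x 0.5 = 3.8 if errors are independent between eyes, or 7.6 x 0.9 = 6.84 if they correlate 0.8. The artefacts are 17.7 x 3.8/123.2 = 0.55 and 17.7 x 6.84/123.2 = 0.98 letter. The other rows scale in proportion:

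| Share of change variance that is noise | Independent errors | Errors correlated 0.8 |
|---|---|---|
| All | 0.55 letter | 0.98 letter |
| Half | 0.27 | 0.49 |
| A quarter | 0.14 | 0.25 |

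**Illustrative rejection rates.** These are simulated with no true association, a median split, and a t test on person means at nominal 5%. With all the variance as noise, rejection at N = 40/50/100 is about 9/11/16% with independent errors and 13/14/26% with errors correlated 0.8. With half as noise it is about 5-10%; with a quarter, about 5-7%.

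**Percent change.** With equal letter loss in all eyes, division by a higher baseline makes the percent loss of better eyes smaller, which works against the artefact. With independent errors, the better-minus-worse gap is about -0.2 points with all the variance as noise and about +0.15 points with half; rejection is 5-6%. It departs clearly from nominal only with all the variance as noise and errors shared between eyes.

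**Separate reading.** With strata from an independent acuity test, the letter gap returns to about 0 and rejection to about 5%.

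**The case against.** The strongest reply is that the stratifier is not fixed as Baseline acuity. It is undated, and the only acuity categories the protocol defines are the Vision Cohorts (2.2), set at the Registry/Screening Visit. Genes enter the NHS one at a time, often well after Registry enrolment, so the two acuities will often be separate tests and the artefact would then be absent. This stands as a limit. It does not settle the matter, because the protocol neither says that Registry acuity is meant nor deals with the participants whose Registry reading becomes Baseline.

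Second, the table is exploratory and names no test. The 0.05 level comes from the generic subgroup power illustration in 9.1.3. Cut-points may properly be left to a statistical analysis plan, which was not available here. This also stands, so the rejection rates are illustrations only. Crossing acuity change with acuity is nevertheless in the protocol's own text.

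A reader might go further and infer that the plan will flag acuity falsely in up to a quarter of larger genes, or that it will generally show faster loss in better-seeing eyes. The documents do not support either inference. The first needs N = 100, essentially no true variation in progression between participants, and errors largely shared between eyes. The second fails on the percent scale, which the same table also reports. Nor is there a basis for extending the point to low-luminance acuity, which is a separate reading.

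**Conclusion.** The point holds as a modest, avoidable bias in one planned table: absolute letter change in acuity by acuity level, when the stratum comes from the reading used as Baseline. Its direction is certain under that condition. Its size is about 0.1 to 1.0 letter for a median split, roughly 8% to 54% of the 1.8-letter mean loss (0.14/1.8 to 0.98/1.8). Even the top of the range is about a third of the example's detectable difference (3.76% x 77.9 = 2.9 letters, an approximate conversion from percent).

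The size rests on an assumed noise share, on acuity and change SDs borrowed from the protocol's reference study, and on comparison with a 24-month loss because no 4-year mean is given. A narrower acuity range within a gene would enlarge the artefact. The case for acting is that correction is cheap, not that the bias is large.

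**What to change.** Add a sentence to NHS Objective 3, for the visual acuity change outcome only: acuity strata are formed from a Registry/Screening acuity that was a separate test from the Baseline acuity. Where no separate reading exists, because the Registry value was reused as Baseline or the participant is in the Younger Age Cohort, either omit acuity as a factor for acuity change or estimate the association between level and slope from a mixed model with correlated random intercept and slope. Keep acuity as a factor for all other outcomes, and date the stratifier. Entering Baseline acuity as a covariate would not help, since it is itself the factor under study.

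The cost is the wording and, under the omission option, the loss of those participants from this one cross-tabulation. No new data are needed. A percent-scale gap of about 0.5 point would remain under equal letter loss even with a separate reading. That reflects division by different baselines rather than test noise, so the two scales should be read with that in mind.

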	if the observed correlation <math>r = 0.3</math>	(0.02, 0.53)	
	if the observed correlation <math>r = 0.5</math>	(0.26, 0.68)	
	if the observed correlation <math>r = 0.8</math>	(0.67, 0.88)	
NHS Objective 3 (Risk Factors for Progression)	A comparison of two equal-sized subgroups (N=25 each group) would have about 80% power to conclude there is a difference if the true difference is		
	Visual Acuity	OCT EZ area	Static Perimetry HOV
	4%	15%	23%*
	[Type I ( $\alpha$ ) error rate of 0.05] * For example, if one subgroup had a percent change of 13%, the other subgroup would need a percent change of 36% to statistically conclude there is a difference.		

1239

1240 **9.2 Data Analysis**

1241 The analysis plans below are written with respect to the majority of outcomes of interest.

1242 Analyses will include data on both eyes for each participant, and confidence intervals will adjust  
1243 for correlation between two (2) eyes of the same participant.

1244 **9.2.1 Registry Data Analysis**

1245 The following Registry data analysis considerations focus on **Registry Objective 2** (see section  
1246 1.3). *Applicability of within-gene objectives will depend on within-gene sample size as noted  
1247 below. If less than 20, limit primary objective to describing the cohort in the form of case  
1248 histories. Objectives may still be explored depending on the needs for a specific gene.*

1249

1250 **Registry Objective 2 (Cross-Sectional Phenotype Characterization)**

1251 ➤ **Registry Objective 2** is to characterize cross-sectional retinal dystrophy associated with  
1252 disease-causing genetic variants using functional and structural measures (visual acuity,  
1253 OCT, static perimetry), **within-gene**. Structure-function relationships and risk factors for  
1254 disease severity will also be explored **within-gene**.

1255 ○ The distribution of each cross-sectional outcome measure will be summarized  
1256 (including tabulating categorically, as well as means, SDs, medians, quartiles,  
1257 ranges; *where sample size 20 or more*).

- 1258 ○ Scatterplots and Spearman correlation coefficients between cross-sectional  
 1259 outcome measures will be explored (*where sample size is 20 or more*)
- 1260 ○ Possible risk factors (genotype, phenotype, environmental, and comorbidities)  
 1261 for cross-sectional outcome measures will be explored (*where sample size is*  

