 1262 *40 or more*).
- 1263 ○ Methods will include univariate and multivariate analysis of  
 1264 covariance (ANCOVA) models. A stepwise selection procedure will  
 1265 be used to build the final model. A threshold of  $P < 0.10$  will be used to  
 1266 add to the model, and a threshold of  $P < 0.05$  will be used to remain in  
 1267 the multivariate model. Linearity of continuous factors will be  
 1268 assessed, and possibly quadratic or cubic terms will be considered if  
 1269 non-linear.
- 1270 ○ Potential risk factors to evaluate include:
- 1271     ▪ Phenotypic:
- 1272         • Clinical diagnosis (if applicable)
- 1273         • Duration of disease
- 1274         • Age of onset of initial vision symptoms
- 1275         • Gender
- 1276         • Race/ethnicity
- 1277         • Visual acuity
- 1278         • Lens Status (phakic/pseudophakic/aphakic)
- 1279     ▪ Genotypic:
- 1280         • Characterizations of the variants
- 1281     ▪ Environmental factors
- 1282         • Smoking status
- 1283         • Vitamin A use
- 1284         • Docosahexaenoic acid (DHA) use
- 1285         • Lutein use
- 1286 ○ Variability of symmetry of left and right eye cross-sectional outcome  
 1287 measures will be evaluated by scatterplots. Bland-Altman plots of the inter-  
 1288 eye difference versus the mean value will be inspected and a linear regression  
 1289 model for the differences will be used to test whether the intercept (overall  
 1290 mean difference) and slope is 0. The plot will be inspected to evaluate whether  
 1291 variability between eyes changes with greater mean values. The intraclass  
 1292 correlation coefficient of the values and the within-person variance will be  
 1293 estimated.

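### NHS Objective 3 relates 4-year change to continuous risk factors only through categories, although the Registry plan keeps such factors continuous

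*Protocol*

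**What the plan says.** Protocol section 9.2.2, NHS Objective 3, summarizes absolute and percent change from baseline to 4 years, "stratified by categorical levels of each potential risk factor". The list that follows includes "Duration of disease", "Age of onset of initial vision symptoms" and visual acuity, next to categorical factors such as gender, lens status and supplement use. No cut-points, test or model are given. The objective applies within gene at 40 or more participants.

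Section 9.2.1, Registry Objective 2, has essentially the same list and the same minimum of 40. There the method is univariate and multivariate ANCOVA. It adds that "Linearity of continuous factors will be" assessed, with quadratic or cubic terms considered if the relation is not linear.

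Section 9.1.3 sizes NHS Objective 3 as a difference in percent change at "four (4) years among two (2) subgroups of equally distributed sizes, under various" assumptions on effect and SD. Its worked example states: "A comparison of two equal-sized subgroups (N=25 each group) would have about 80% power" for true differences of 4% (visual acuity), 15% (OCT EZ area) and 23% (static perimetry HOV).

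**The concern.** The protocol treats the same variables in two ways. The cross-sectional analysis uses the full scale of a continuous factor. The 4-year analysis, which is meant to help define subpopulations for later trials, is described only in categories, and no reason is given.

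Cutting a continuous factor discards information on any graded relation with outcome. With 40 to 100 participants per gene, and patients who cannot be replaced, little can be spared. A real predictor such as disease duration is more easily missed. Because cut-points are not stated, the picture can also depend on where the cut falls and may not be comparable across genes.

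**Working it through.** **Inputs.** All come from the section 9.1.3 example: N=50 in two groups of 25; "Inter-eye correlation = 0.8", so the multiplier is 2/(1+0.8) = 1.11, effective N is 55.6 and there are 27.8 per group; Type I "error rate of 0.05" (sidedness not stated; two-sided reproduces the figures); SDs of 5%, 20% and 30%; differences of 4%, 15% and 23%.

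**Step 1: the protocol's own figure.** Two-sample t comparison, noncentrality d × √(27.8/2), where d is difference/SD.
- Visual acuity: d = 4/5 = 0.80, power 0.833
- EZ area: d = 15/20 = 0.75, power 0.784
- HOV: d = 23/30 = 0.767, power 0.801

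This reproduces the stated 80% or so. The difference detectable with exactly 80% power is 0.766 SD, i.e. 3.8%, 15.3% and 23.0%.

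**Step 2: the same relation with the factor kept continuous.** Assumptions that are not in the protocol: the factor is roughly normal, its effect is linear, and the two equal groups are a median split of it. Such a split multiplies the correlation by √(2/π) = 0.798, so it keeps 2/π, about 64%, of the information.
- Correlation after the split: d/√(d²+4) = 0.371, 0.351, 0.358
- Underlying correlation (divide by 0.798): 0.465, 0.440, 0.449
- Fisher z power, Φ(atanh(r) × √(55.6−3) − 1.96): 0.955, 0.928, 0.938

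A shorter route starts from exactly 80% power, where the noncentrality is 2.80: Φ(2.80/0.798 − 1.96) = 0.940. With a noncentral-t regression in place of Fisher z, the HOV case gives 0.957. For a uniform factor the split factor is √3/2 = 0.866, and Φ(2.80/0.866 − 1.96) = 0.90. The range is therefore about 90% to 96%.

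**Step 3: other ways to use the categories.** Simulation with a normal factor, linear effect r = 0.449, N = 56:

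| Analysis | Power |
|---|---|
| Continuous | 0.94 |
| Median split | 0.80 |
| Trend over 3 levels | 0.88 |
| Trend over 4 levels | 0.90 |
| Trend over 5 levels | 0.91 |

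The gain over an ordered-category trend test is 0.94 − 0.91 to 0.94 − 0.88, i.e. 3 to 6 points. An unordered F test over three or four groups does no better than the split in any useful way (0.76 to 0.84 for r of 0.44 to 0.47).

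**Step 4: when the relation is not linear.** Suppose the truth is a step of 0.766 SD at the median. The split then has its full correlation of 0.358, and the linear term sees 0.358 × 0.798 = 0.285. Fisher z gives Φ(atanh(0.285) × √52.6 − 1.96) = 0.57; simulation at N = 56 gives 0.59, against 0.80 for the split. The linear term is about 21 points worse here.

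**The case against.** The strongest reply is that section 9.2.2 describes a table. It says that distributions will be summarized and names no test or p-value, so it has no power to lose. The 80% belongs to a planning example in 9.1.3, a section that calls itself simplified and does not mention splitting a continuous factor. A continuous model could be added in a statistical analysis plan that is not shown, and nothing in 9.2.2 forbids one. The objective is also explicitly exploratory, and most of the listed factors are categorical anyway.

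Much of this stands. A reader might infer that Objective 3 will be tested by a median split and so gives up 14 points of power. The protocol does not support that: it specifies neither two levels nor a split, and how duration and age of onset are recorded is not stated. Nor is a continuous linear term always better, as the step case shows.

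What does not stand is that the protocol is merely silent. It states an analysis plan for this objective, that plan works by categorical level for each factor, and it differs from what section 9.2.1 does with essentially the same factors. Section 9.1.3 also speaks of power to detect subgroup differences, so some inference from Objective 3 is expected.

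**Conclusion.** The point holds in a limited form. Section 9.2.2 puts continuous factors on a coarser scale than section 9.2.1 does, without a reason, and the approach in 9.2.1 could be carried over.

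The size is conditional. It is about 80% against 94% (range about 90-96%) only if inference follows the two-equal-subgroup comparison of 9.1.3, applied as a median split to a roughly normal factor with a linear effect. It is about 3-6 points against a trend test over three to five ordered levels. It reverses, at about 59% against 80%, if the true relation is a step at the median. The point covers duration of disease, age of onset and visual acuity; factors that are categorical by nature are not touched. For an exploratory objective this is a worthwhile improvement and does not invalidate the plan.

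**What to change.** In section 9.2.2, NHS Objective 3, add a model of 4-year change in which continuous factors (duration of disease, age of onset, visual acuity) enter as continuous terms. Assess linearity and consider non-linear terms as already written in 9.2.1, and handle inter-eye correlation as in 9.2. Keep the stratified tables as descriptive displays; they also help to reveal a threshold pattern that a linear term would miss. Leave categorical factors as they are.

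The cost is one or two sentences and some extra analysis work, with no new data, visits or participants. The downside is lower power for the linear term if the true relation is a threshold, which the linearity check and the retained tables limit but do not remove.
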